3.2.4 Rationale for MHAA4549A Dosage

[figure not shown]
A single IV dose of 3600 mg of MHAA4549A was selected to assess the efficacy of MHAA4549A and to provide data for further clinical development. The selection of dose

in this study for severely ill patients was based on the observed human pharmacokinetics in Phase 1 and the relationship between the pharmacokinetics, pharmacodynamics, and efficacy observed in a Phase 2a human challenge model of influenza. MHAA4549A was shown to be safe and well-tolerated at all dose levels (ranging from 1.5 mg/kg to 45 mg/kg for Phase 1 and 400-3600 mg for Phase 2a) through a follow-up period of 120 days post-dose in the Phase 1 and Phase 2a study. The dose level used in this study was determined following analysis of data from the Phase 2a study, GV28985, which demonstrated the following:

- The 3600-mg dose demonstrated a significant decrease in viral shedding in upper respiratory samples. Based on current interim analysis data, there was a 97.5% ($p=0.0051$) decrease in AUEC and a 77.3% decrease in peak viral load by qPCR measurement compared to the placebo group.
- Symptom data in the Phase 2a study showed a decrease in the AUC of symptoms scores for the 3600-mg dose, as illustrated in Table 1, which is consistent with the virological results.
- The 1200-mg dose level was not efficacious
- There are no safety concerns at the 3600-mg dose level to date.
- Hospitalized patients generally have a longer duration of viral shedding and significantly more viral burden in the lower lung compartments; therefore, high concentrations of mAb are likely needed to achieve sufficient occupancy of the virus binding sites in the upper and lower respiratory compartments. Furthermore, higher concentrations of mAb are necessary to mitigate the risk of resistance for MHAA4549A .

The Phase 1 study was conducted using body-weight based dosing followed by a fixed dosing strategy that was used in the Phase 2a study. Thus, the fixed dosing regimen that was used in the Phase 2a study will be used for this study, given the practical advantages and positive safety profile of MHAA4549A to date. Further, fixed dosing is generally recommended with monoclonal antibodies, due to their minimal PK variability (Bai et al. 2012). The PK variability introduced by different dosing regimens (i.e., body-weight based dosing versus fixed dosing) is moderate relative to the variability generally observed in pharmacodynamics, efficacy, and safety and would not be expected to be clinically meaningful.

3.2.5 Rationale for Biomarker Assessments

3.3 OUTCOME MEASURES

3.3.1 Safety Outcome Measures

The safety outcome measures for this study are as follows:

- Adverse events and clinical laboratory abnormalities
- Vital signs, physical findings, ATAs, and clinical laboratory results during and following administration of MHAA4549A

3.3.2 Primary Efficacy Outcome Measure

The primary outcome measure for this study is as follows:

- Time to normalization of respiratory function defined as:
 - The time to cessation of O₂ support resulting in a stable SpO₂ >95% for at least 24 hours (see [Appendix 2](#) for details)

3.3.3 Secondary Efficacy Outcome Measures

The secondary efficacy outcome measures for this study are as follows:

- Clinical failure after 24 hours post-infusion of study drug; defined as:
 - Progression to increased O₂ requirement defined by an increase in oxygen supplementation from low flow oxygen (2–6 L/min) to high flow oxygen (>6 L/min) or from oxygen supplementation alone to any PPV
 - Progression to ICU
 - Prolonged ventilation or O₂ support defined by >2 weeks, or
 - Death
- Time to clinical normalization of vital signs (3/5 criteria must be met):
 - SpO₂ > 95% without supplemental O₂ for at least 24 hours
 - Core temperature < 37.2°C immediately prior to receipt of any antipyretic drug, and at least 6-8 hours from the last dose of antipyretic or core temperature >36°C in patients who are initially hypothermic
 - Heart rate (HR) < 100/minute
 - Systolic blood pressure (SBP) > 90 mmHg
- All-cause mortality at Day 14, Day 30, and Day 60
- Influenza A viral load in nasopharyngeal samples
 - AUEC
 - Peak viral load

- Time to resolution of infection
- Duration of hospitalization
- Duration of ICU stay
- Antibiotic usage for respiratory infections
- Complications of influenza:
 - Pneumonia (HAP/VAP)
 - Exacerbations of chronic lung disease
 - Myocarditis
 - ARDS
 - Otitis media
 - Other related complications
- All-cause readmission at Day 30 and Day 60
- Duration of ventilation

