Safety Outcome Measures

The safety outcome measures for this study are as follows:

- Adverse events and clinical laboratory abnormalities
- Vital signs, physical findings, ATAs, and clinical laboratory results during and following administration of MHAA4549A

Efficacy Outcome Measures

The primary outcome measure for this study is as follows:

- Time to normalization of respiratory function defined as:

– The time to cessation of O₂ support resulting in a stable SpO₂>95% for at least 24 hours
The secondary efficacy outcome measures for this study are as follows:

- Clinical failure after 24 hours post-infusion of study drug defined as:
 - Progression to increased O₂ requirement defined by an increase in oxygen supplementation from low flow oxygen (2–6 L/min) to high flow oxygen (> 6 L/min) or from oxygen supplementation alone to any PPV
 - Progression to ICU
 - Prolonged ventilation or O₂ support defined by > 2 weeks, or
 - Death
- Time to clinical normalization of vital signs (3/5 criteria must be met):
 - SpO₂>95% without supplemental O₂ for at least 24 hours
 - Respiratory rate < 24 breaths per minute without supplemental O₂ for at least 24 hours
 - Core temperature < 37.2°C immediately prior to receipt of any antipyretic drug, and at least 6-8 hours from the last dose of antipyretic or core temperature > 36°C in patients who are initially hypothermic
 - Heart rate (HR) < 100/minute
 - Systolic blood pressure (SBP) > 90 mmHg
- All-cause mortality at Day 14, Day 30, and Day 60
- Influenza A viral load in nasopharyngeal samples
 - Area under viral load–time curve (AUEC)
 - Peak viral load
 - Time to resolution of infection
- Duration of hospitalization
- Duration of ICU stay
- Antibiotic usage for respiratory infections
- Complications of influenza:
 - Pneumonia (HAP/VAP)
 - Exacerbations of chronic lung disease
 - Myocarditis
 - Acute respiratory distress syndrome (ARDS)
 - Otitis media
 - Other related complications
- All-cause readmission at Day 30 and Day 60
- Duration of ventilation

Pharmacokinetic Outcome Measures

The primary PK outcome measures for this study are as follows:

- PK parameters for MHAA4549A in serum including total exposure (i.e., AUC), maximum observed concentration (C_{max}), clearance, half-life, and volume of distribution, when appropriate, as data allow

The exploratory PK outcome measures for this study are as follows:

█ [REDACTED]

█ [REDACTED]

Exploratory Outcome Measures

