6.4.2 Secondary Efficacy Endpoints

- Proportion of patients with clinical failure after 24 hours post-infusion of study drug
- Median time to clinical resolution of vital signs
- Hazard ratio for mortality at Day 14, Day 30, and Day 60
- Mean and median AUC of viral load
- Mean and median peak viral load
- Median duration of viral shedding in upper respiratory samples
- Median duration of hospitalization
- Median duration of ICU stay
- Proportion of patients requiring antibiotics for respiratory indications during study

- Proportion of patients with influenza secondary complications
- Median duration of ventilation
- Proportion of patients who are readmitted by Day 30 and Day 60

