- ^h Concomitant medications should be recorded for 30 days prior to screening, through the study completion/early discontinuation visit. See exclusion criteria in [Section 4.5.2](#) for prohibited therapies.
- ⁱ Vital signs will be collected within 1 hour before MHAA4549A infusion and within 1 hour after completion of MHAA4549A infusion include temperature, respiratory rate, heart rate, systolic blood pressure, and diastolic blood pressure. Temperature should be measured using the same methodology throughout the study and should be measured prior to administration of any antipyretic drugs. In patients who have multiple vital signs taken during any day, the most abnormal value should be recorded from that 24-hour period. Temperature, blood pressure, respiratory rate, and heart rate will be completed after the patient has been supine for > 5 minutes. The worst/most abnormal value from the last 24-hour period should be recorded for patients who are in the ICU.
- ^j APACHE scores are optional and only for patients that are in the ICU. For calculation of the screening APACHE score, the worst values in the preceding 24 hours should be used. APACHE scores are not required for study conduct or entry but should be collected if available.
- ^k SOFA scores are only for patients in the ICU that have available data such as PaO₂/FiO₂ (mmHg). See Appendix 7 for SOFA score calculation.
- ^l Patient should rest in a supine position for 10 minutes prior.
- ^m Patient will be a resident for at least 24 hours following administration of MHAA4549A.
- ⁿ Oseltamivir must be given for a minimum of 5 days. Treatment longer than 5 days is permitted based on the discretion of the investigator [indicated by (x)].

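### The temperature component of vital-sign normalization has no upper limit for initially hypothermic patients, and its antipyretic interval is a range rather than one cut-off.

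*Combined protocol and SAP*

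**What the plan says.** Section 3.3.3 of Version 3 (VHP Only) defines the secondary endpoint as "Time to clinical normalization of vital signs (3/5 criteria must be met"). Its temperature component has two branches:

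- **General branch:** "Core temperature < 37.2°C immediately prior to receipt of any antipyretic drug", combined with a minimum time since the last antipyretic.
- **Hypothermic branch:** joined to the first by the word or. The full run is "at least 6-8 hours from the last dose of antipyretic or core temperature >36°C in patients who are initially hypothermic".

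The Version 3 synopsis repeats the component: "at least 6-8 hours from the last dose of antipyretic or core temperature > 36°C in patients who are initially hypothermic". The original protocol and Version 2 carry the same wording in both places.

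Two footnotes to Appendix 1a and 1b bear on the measurement. In Appendix 1a, "Temperature should be measured using the same methodology throughout the study and should be measured prior to administration of any antipyretic drugs", and when several readings exist in a day, "the most abnormal value should be recorded from that 24-hour period". Neither footnote gives a normal range or a single antipyretic interval. Section 6.4.2 lists the summary as "Median time to clinical resolution of vital signs". Section 6 says that no formal hypothesis testing will be done.

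**The concern.** The component is meant to detect a return to normal temperature. For a patient who enters hypothermic, the branch written for that patient sets only a floor. Rewarming past 36°C satisfies it, and so does overshooting into high fever. Appendix 8 of the same protocol grades 39.0–40.0°C as Grade 3 (severe) fever, so one reading can be severe in the safety tables and normalized in the efficacy endpoint.

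The antipyretic interval is a second, separate problem. A minimum has to be one number, and two programmers could each follow the text and derive different event times.

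What is at stake is misclassified event times. Three criteria complete the event. The heart-rate and blood-pressure criteria carry no duration requirement, so those two plus a wrongly passed temperature can complete it in a patient who is still on oxygen.

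**Working it through.** There is no stated figure to reproduce. The check treats the component as a logical rule.

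**Inputs.** All come from Section 3.3.3 and the synopsis of Version 3: upper limit 37.2°C (general branch), lower limit 36°C (hypothermic branch), and an antipyretic interval with a minimum of 6 or 8 hours. Let T be the temperature, h the hours since the last antipyretic, and c the cut-off (6 or 8).

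**Two readings of the sentence.**

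- Literal OR: met if (T < 37.2 and h ≥ c), or (initially hypothermic and T > 36).
- Branch by baseline status: if initially hypothermic, met if T > 36; otherwise met if T < 37.2 and h ≥ c.

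**Results.**

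| Patient | T (°C) | h | c | Literal OR | Branch by baseline |
|---|---|---|---|---|---|
| Initially hypothermic | 39.5 | 7 or 12 | 6 or 8 | met | met |
| Initially hypothermic | 35.0 | 12 | 8 | met | not met |
| Initially hypothermic | 36.8 | 12 | 8 | met | met |
| Not hypothermic at entry | 36.8 | 7 | 6 | met | met |
| Not hypothermic at entry | 36.8 | 7 | 8 | not met | not met |
| Not hypothermic at entry | 39.5 | 12 | 8 | not met | not met |

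1. *Missing ceiling.* The 39.5°C reading passes under both readings of the sentence, so this result does not depend on how the or is parsed.
2. *Literal OR.* Because 36 < 37.2, every T satisfies T < 37.2 or T > 36. Once h ≥ c, an initially hypothermic patient therefore meets the component at every temperature, including an unchanged 35.0°C. Branching by baseline removes this second defect but not the first.
3. *Interval.* At h = 7, the same 36.8°C reading passes with c = 6 and fails with c = 8. Only readings below 37.2°C taken at 6 ≤ h < 8 are affected.

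**Recording rule.** Keeping the worst daily value does not help, because the rule accepts 39.5°C when that is the worst value.

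**Effect on the composite.** Temperature changes a three-criteria event only when exactly two of the other criteria are met.

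- Section 3.3.3 lists three other criteria: 3 of 2³ = 8 patterns have exactly two met.
- The synopsis lists four others, since it includes respiratory rate: 6 of 2⁴ = 16 patterns.

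These are counts of patterns, not probabilities. The event time also moves only if three criteria had not already been met earlier. The two lists differ under the same three-of-five rule and must be reconciled in any case.

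**After the change** (36 < T < 37.2 for initially hypothermic patients): 39.5°C is not met, 35.0°C is not met, and 36.8°C is met.

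**The case against.** The strongest reply is that intent is obvious. No sensible programmer would score 39.5°C as normalized, and every criterion in the composite is one-sided because each tests recovery from the expected direction of abnormality. That has force for patients who were not hypothermic at entry. For them, the absence of a floor (a fall to 35.0°C passes, given the antipyretic interval) is in line with a heart-rate criterion that has no lower limit and a blood-pressure criterion that has no upper limit. A 36°C floor for everyone is therefore a preference. It does not answer the hypothermic branch, where the text states a rule that gives a wrong score and nothing available overrides it.

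Three stronger readings are tempting, and the documents do not support them.

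- *That a patient at 39.5°C counts as recovered.* Only one component is met, and two other criteria are still needed.
- *That every error makes sick patients look resolved early.* This holds for the missing ceiling but not for the interval. With an 8-hour bound, an afebrile patient dosed every 6 hours could fail repeatedly, which can delay the event.
- *That the number of affected patients can be estimated.* No hypothermia rate is given. Assuming 2% to 10% of the 300 evaluable patients in Section 6.1 gives 300 × 0.02 = 6 to 300 × 0.10 = 30 patients to whom the branch applies. That is not a count of changed event times, and no shift in the median follows from it.

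It also stands that the rule is the same in both arms of a randomized, double-blind study, so no between-arm bias is shown.

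**Conclusion.** The point holds in limited form. In Version 3 the component gives a wrong score for initially hypothermic patients with a later high temperature. Under a literal OR, it is no test at all for those patients once the antipyretic interval has passed. The interval is ambiguous for readings taken 6 to 8 hours after a dose, with effects in either direction.

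The consequence is some misclassified event times on a secondary endpoint. Since no formal hypothesis testing is planned, type I error and power are not at issue. The effect is probably small, but this is a judgement: the documents give neither a hypothermia rate nor the frequency of antipyretic use.

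The conclusion rests on Version 3. The available text of Version 5 (Global) ends within its amendment rationale, and no separate SAP was available, so a later correction can be neither confirmed nor excluded.

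**What to change.** First check Section 3.3.3 of Version 5 and the SAP. If the wording is unchanged, rewrite the component for endpoint scoring only, identically in Section 3.3.3, the synopsis and the SAP:

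- Initially hypothermic patients meet it only when temperature is both above 36°C and below 37.2°C, which are the protocol's own limits.
- State which baseline value makes a patient initially hypothermic, as no threshold is given, and whether the antipyretic conditions apply to these patients.
- Replace the range of hours with one interval of the sponsor's choosing. Fix it before any unblinded interim analysis. Section 6.7 allows up to two interim efficacy analyses by sponsor staff unblinded at group level, and Section 6 already has the SAP finalized before the first.

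Applying the 36°C floor to all patients is optional.

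The cost is one line in each document. Temperature and concomitant medications are already collected, and patient care does not change. The downside is slightly later event times in a few patients.

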4.5 CONCOMITANT THERAPY AND FOOD

4.5.1 Permitted Therapy

Concomitant medication includes any medication (e.g., prescription drugs, over-the-counter drugs, herbal or homeopathic remedies, nutritional supplements) used by a patient from 30 days prior to screening to the study completion/discontinuation visit. All concomitant medications should be reported to the investigator and recorded on the Concomitant Medications eCRF. For any NAIs (e.g., oseltamivir, peramivir, zanamivir, laninimavir) that have been taken prior to study drug therapy, the number of doses and duration of therapy must be recorded.

Patients who use oral contraceptives, hormone-replacement therapy, or other maintenance therapy should continue their use.

All therapies required for management of the patient's acute illness are permitted except for those listed below in [Section 4.5.2](#).

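### The vital-signs secondary endpoint credits SBP above 90 mmHg with no condition on vasopressor or inotrope support, so a drug-held pressure can supply one of the three criteria needed

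*Combined protocol and SAP*

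**What the plan says.** Section 3.3.3 introduces the endpoint as "Time to clinical normalization of vital signs (3/5 criteria must be met". The criteria treat support differently:

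- Saturation: "SpO₂ > 95% without supplemental O₂ for at least 24 hours".
- Respiratory rate: "Respiratory rate < 24 breaths per minute without supplemental O₂ for at least 24 hours". This item is in the Version 3 synopsis but missing from the Version 3 list in Section 3.3.3, which names four items under a three-of-five rule.
- Temperature: "Core temperature < 37.2°C immediately prior to receipt of any antipyretic drug, and at least 6-8 hours from the last dose of antipyretic". An alternative branch for initially hypothermic patients has no antipyretic condition.
- Heart rate: "Heart rate (HR) < 100/minute".
- Blood pressure: "Systolic blood pressure (SBP) > 90 mmHg".

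Section 4.5.1 says that therapies needed to manage the patient's "acute illness are permitted except for those listed below", and the list in Section 4.5.2 covers certain antivirals and probenecid, not vasopressors or inotropes. The vital-signs footnote to Appendix 1a adds: "In patients who have multiple vital signs taken during any day, the most abnormal value should be recorded from that 24-hour period". It repeats the worst-value instruction for patients in intensive care. Sections 4.6.6, 6.4 and 6.4.2 give no rule for blood pressure measured under drug support.

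**The concern.** The conditions on saturation, respiratory rate and temperature show what the endpoint is meant to measure: recovery that is not produced by the support being given. The blood-pressure criterion departs from that. In a patient on a continuous vasopressor, a systolic pressure above 90 mmHg reflects the infusion at least as much as the patient.

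The endpoint is analysed as a time to event, and neither blood pressure nor heart rate has a required duration. One qualifying day can therefore end a patient's follow-up for this endpoint. The patients affected are among the sickest, and they would be recorded as early recoveries. If support is used equally in both arms, such events would be expected to blur a difference between them. If use differs by arm, they could bias the comparison.

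One stated goal of the study is to find suitable endpoints for hospitalized influenza, so the behaviour of a component matters beyond this trial's own comparison.

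**Working it through.** The plan states no figure on this point, so there is none to reproduce. The check is on the scoring rule.

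**1. How often blood pressure can decide the result.** With the five criteria in the synopsis, the minimal ways to pass are the sets of three: C(5,3) = 10. Those that include blood pressure number C(4,2) = 6. With only the four items in the Version 3 Section 3.3.3, there are C(4,3) = 4 sets, of which C(3,2) = 3 include it.

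**2. Which sets a patient on oxygen or ventilation can reach.** Saturation and respiratory rate both require being off supplemental oxygen. Without them, three criteria remain: temperature, heart rate and blood pressure. That is exactly one set, and it is the same under the five-item and four-item lists. It contains both haemodynamic criteria, neither of which has a condition on support.

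**3. A patient who passes.** Take 37.0°C before any antipyretic and outside the antipyretic interval, a worst heart rate of 95/minute, and a worst systolic pressure of 95 mmHg on a stable vasopressor infusion. The three tests are 37.0 < 37.2, 95 < 100 and 95 > 90. All are met, so the patient is scored as normalized.

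**4. Whether the recording rule prevents it.** On the day a hypotensive reading prompts an infusion, that reading is the most abnormal of the 24 hours, so the criterion is not met. On a later day, if the infusion keeps every reading above 90, the most abnormal value is also above 90 and the criterion is met. The rule protects the first day but not sustained support.

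**5. Possible size.** The documents give no rate of vasopressor use. Their nearest figures are a 45% cap on enrolled patients receiving positive pressure ventilation and a cited 27% intensive-care admission rate; neither measures vasopressor use. Assuming 5% to 20% of 300 evaluable patients:

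- 300 × 0.05 = 15
- 300 × 0.20 = 60

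These are patients whose blood-pressure criterion would be drug-supported at some time. A false resolution also needs two further criteria met on the same supported day, so the number misclassified is smaller and cannot be derived from the documents.

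**6. Effect of the change.** If blood pressure cannot count on supported days, 10 − 6 = 4 sets remain under the five-item list and 4 − 3 = 1 under the four-item list. The set in step 2 is no longer available on those days.

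**The case against.** The strongest reply is that the three-of-five rule does most of the damage. A ventilated patient with the same temperature, heart rate and pressure and no vasopressor would also pass. If all five criteria were required, only vasopressor-dependent patients already off oxygen for 24 hours would remain, probably a small group. This stands as a limit on size: the consequence depends heavily on the lenient rule, and conditioning blood pressure does not repair that rule. It does not make the component sound, because a drug-held pressure would still count under any number of required criteria.

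Several stronger readings are tempting but not supported:

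- A reader might infer that starting a vasopressor during deterioration at once turns a failed criterion into a met one. The most-abnormal-value rule prevents that on the day of the hypotensive reading.
- A reader might take 15 to 60 as the number of false resolutions. It is an assumed count of patients on support.
- A reader might say that the plan expressly accepts pressure on vasopressors. It is silent; the criterion is met as written because nothing excludes it.
- Blood pressure is not the only unconditioned item: heart rate and the hypothermia branch of the temperature criterion are too.

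It is also fair to say that this is one component of one of many secondary endpoints, in a study that plans no formal hypothesis testing. Deterioration is also captured through clinical failure, time in intensive care and mortality. That bears on priority and does not correct the scoring.

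**Conclusion.** The point holds in a limited form. As written, the endpoint lets a systolic pressure sustained by vasopressors or inotropes count towards normalization. With the temperature and heart-rate criteria also met, such a patient is scored as recovered, including while ventilated. This can happen on days of stable support after the day of hypotension.

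The number affected cannot be estimated from the documents. Under an assumed 5% to 20% use it is some number below 15 to 60 of 300, and no effect on the median or hazard ratio can be calculated. The primary endpoint, sample size and power do not depend on it. It is a worthwhile, inexpensive improvement to a secondary endpoint.

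The conclusion rests on the protocol text through Version 3. A Version 5 (Global) exists, but only its title page and the start of its amendment rationale could be read. Section 6 defers analysis detail to a SAP that was also not available. Either may already contain a rule.

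**What to change.** Check the Version 5 protocol and the SAP for an existing rule. If there is none, state in Section 3.3.3, the synopsis and the SAP that the blood-pressure criterion is scored as not met on any study day with vasopressor or inotrope use. Derive those days from start and stop dates on the Concomitant Medications eCRF, and fix the rule and the list of qualifying drugs before unblinding. In the same edit, reconcile the four-item list in Section 3.3.3 with the five-item list in the synopsis.

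The change affects scoring only, with no effect on treatment, visits or sample size. It costs one sentence in each place and one derived variable. There are two small downsides. Infusion dates must be complete, which may mean extra queries. Day-level scoring is also slightly conservative, because a patient weaned early in a day does not get credit until the next. The change leaves heart rate and the hypothermia branch as they are; the SAP should say whether that is intended.
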